6.3.7. Endpoints Related to Infectious Titer

The analyses for the following endpoints related to infectious titer will be specified in virology analysis plan.

- Time to negative infectious titer by TCID50 in participants with detectable viral titers at baseline by TCID50.
- Change in TCID50 from baseline to Days 3, 5, 10, 15, 21, 28, and 34 in participants with detectable viral titers at baseline by TCID50.
- Proportion of participants with negative infectious titer by TCID50 on Days 3, 5, 10, 15, 21, 28, and 34 in participants with detectable viral titers at baseline by TCID50.
- Time to negative infectious titer by virus recovery in participants with positive viral titers at baseline by virus recovery.
- Proportion of participants with negative infectious titer by virus recovery on Days 3, 5, 10, 15, 21, 28, and 34 in participants with positive viral titers at baseline by virus recovery.

6.3.8. Change from Baseline in SARS-CoV-2 Viral RNA Level in Plasma, Over Time

Change from baseline in SARS-CoV-2 viral RNA level in plasma, over time will be analyzed similar to the primary endpoint using MMRM model in mITT analysis set. The LS means and treatment difference for each visit will be calculated and presented with their corresponding 95% CIs.

6.3.9. Proportion of Participants with COVID-19-related Hospitalization >24h or Death from Any Cause through Day 28

The number and proportion of participants with COVID-19-related hospitalization >24h or death from any cause through Day 28 will be summarized by treatment group. The analyses will be done using the mITT analysis set.

6.3.10. Number of COVID-19-related Medical Visits through Day 34

Number of COVID-19-related medical visits through Day 34 will be summarized by treatment group descriptively (n, mean, standard deviation, median, min, max). The analysis will be done using the mITT analysis set.

6.3.11. Time (days) to Sustained Resolution of All Targeted Signs and Symptoms through Day 28

Sustained resolution of all targeted COVID-19 signs/symptoms is defined as the event occurring on the first of 2 consecutive days when all targeted COVID-19 symptoms are scored as absent. The first day of the 2 consecutive-day period will be considered the First Event Date.

For symptoms with no reported severity in baseline, the symptom will have to be absent in order to be counted as sustained resolution (missing severity at baseline will be treated as mild).

Day 27 is the last possible day that symptom resolution can be achieved (definition includes data from the subsequent day) and Day 28 is the last day participants report their daily signs and symptoms.

The time to sustained symptom resolution for the purpose of this study is defined as:

- For a participant with sustained symptom resolution, time to event will be calculated as (First Event Date) – (First Dose Date) +1.
- For a participant that either completes Day 28 of the study or discontinues from the study before Day 28 without sustained symptom resolution (censored), censoring date will be at the last date on which symptom resolution is assessed, and time will be calculated as (Censoring Date) – (First Dose Date) +1 or Day 27 whichever occurs first.

Participants who are hospitalized for the treatment of COVID-19 or die from any cause during the 28-day period will be classified as not achieving sustained symptom resolution and will be censored at day 27.

Time to sustained symptom resolution will be analyzed similarly as in [Section 6.2.2](#).

6.3.12. Other analyses

For the rapid antigen test and NP swab SARS-CoV-2 RNA/RT-PCR test that are collected on the same study day, the concordance analysis will be performed at each visit, across post-baseline visits and across all visits for the each treatment group and overall/combined treatment group in mITT1 analysis set. Kappa statistic will be provided as a measurement of agreement between rapid antigen test and RT-PCR for across post-baseline visits and across all visits.

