Visit Window	Day -1 to Day 1	0 days	±1 day	±1 day	±1 day	±2 days	±2 days	±2 days	±3 days	±7 days	±7 days	±5 days		
 Screening procedures may be done from Day -1 to Day 1 and may be completed on the same calendar day as Baseline/Day 1 procedures. If screening and baseline visits are conducted on the same calendar day, assessments and procedure that are listed to occur at both visits only need to be completed once.
														
 testing will be done at regularly scheduled onsite visits. See Section 8.1.3
Oropharyngeal samples for SARS-CoV-2 RNA level		X		X		X		X	X			X		
 See Section 8.7.4.
Plasma collection for SARS-CoV-2 RNA level		X	X	X	X	X	X	X			X			
 See Section 8.7.2.
Plasma collection specific for biomarkers		X		X		X		X	X			X		
 See Section 8.7.6.1.
Retained research samples for genetics (Prep D1)		X		X		X			X			X		
 If not collected on the designated collection day, collect at the next available time point when biospecimens are being collected in conjunction with a participant visit. See Section 8.6.2.
Retained research samples for biomarkers (Prep B2.5, Prep R1), M3 (urine)		X		X		X			X			X		
 See Section 8.7.8
Study Intervention														
Randomization		X												

Table 1. Study Schedule of Assessment

Visit Identifier	Screen	Treatment Period				Efficacy and Safety Follow-up Period					LTFU			Notes
		Baseline (Day 1)	Day 3	Day 5	Day 10	Day 15	Day 21	Day 28	Day 34	Week 12	Week 24	ET (prior to Day 34)		
Abbreviations used in this table may be found in Appendix 12 .														
 Day relative to start of study intervention (Day 1). Baseline (Day 1) visit is a mandatory visit. Assessments indicated in brackets [X] are only to be conducted if indicated as described in the “Notes”.
Visit Window	Day -1 to Day 1	0 days	±1 day	±1 day	±1 day	±2 days	±2 days	±2 days	±3 days	±7 days	±7 days	±5 days		
 Screening procedures may be done from Day -1 to Day 1 and may be completed on the same calendar day as Baseline/Day 1 procedures. If screening and baseline visits are conducted on the same calendar day, assessments and procedure that are listed to occur at both visits only need to be completed once.

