2.4. Sample Size Determination

The study will enroll approximately 411 participants.

The sample size calculation is based on the primary efficacy endpoint as the change in viral RNA level from baseline to Day 5 as measured in NP swabs in the MITT analysis set. Assuming a SD of 1.8 (based on EPIC-HR, NCT04960202), a sample size of approximately 315 evaluable participants (210 participants in nirmatrelvir/ritonavir group and 105 participants in placebo/ritonavir group) is expected to provide 90% power to detect a difference of 0.7 \log_{10} copies/mL in viral RNA between groups using a 2-sided 0.05 alpha level test. Assuming approximately 10% of participants will have a negative viral RNA result at baseline, and assuming a non-evaluable rate of 15%, approximately 411 participants will be randomized in the study to achieve approximately 315 participants evaluable for the primary efficacy endpoint.

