3.3. Tertiary/Exploratory Endpoint(s)

- Proportion of participants with SARS-CoV-2 RNA in NP swab below the LLOQ on Days 3, 5, 10, 15, 21, 28, and 34.
- Proportion of participants with sustained NP swab SARS-CoV-2 RNA below the LLOQ (defined as $<2.0 \log_{10}$ copies/mL) from Day 5 through Day 34.
- Proportion of participants with SARS-CoV-2 RNA in NP swabs below the LLOQ (defined as $<2.0 \log_{10}$ copies/mL) on both Days 5 and 10.
- The change in SARS-CoV-2 RNA level in NP swabs from baseline to Days 3, 10, 15, 21, 28, and 34.
- Time to sustained NP swab SARS-CoV-2 RNA below the LLOQ (defined as $<2.0 \log_{10}$ copies/mL) and remains below the LLOQ through Day 34 for participants with NP swab SARS-CoV-2 RNA greater than or equal to the LLOQ at baseline.
- Rebound in SARS-CoV-2 RNA level in NP swabs at follow-up (ie, any study visit from Day 10 to through Day 34, defined as a half (0.5) \log_{10} copies/mL increase or greater in SARS-CoV-2 RNA level relative to SARS-CoV-2 RNA level on Day 5 and with a follow-up viral RNA level $\geq 2.5 \log_{10}$ copies/mL.
- Time to negative infectious titer by TCID50 in participants with detectable viral titers at baseline by TCID50.
- Change in TCID50 from baseline to Days 3, 5, 10, 15, 21, 28, and 34 in participants with detectable viral titers at baseline by TCID50.
- Proportion of participants with negative infectious titer by TCID50 on Days 3, 5, 10, 15, 21, 28, and 34 in participants with detectable viral titers at baseline by TCID50.
- Time to negative infectious titer by virus recovery in participants with positive viral titers at baseline by virus recovery.
- Proportion of participants with negative infectious titer by virus recovery on Days 3, 5, 10, 15, 21, 28, and 34 in participants with positive viral titers at baseline by virus recovery.

- Change from baseline in SARS-CoV-2 viral RNA level in plasma, over time.
- Proportion of participants with COVID-19-related hospitalization >24h or death from any cause through Day 28.
- Number of COVID-19-related medical visits through Day 34.
- Time (days) to sustained resolution of all targeted signs and symptoms through Day 28 where sustained resolution is defined as the first of two consecutive days when all targeted COVID-19 symptoms are scored as absent.

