4. ANALYSIS SETS (POPULATIONS FOR ANALYSIS)

Data for all participants will be assessed to determine if participants meet the criteria for inclusion in each analysis population prior to unblinding and releasing the database and classifications will be documented per standard operating procedures.

Population	Description
Full analysis set (FAS)	All participants randomly assigned to study intervention.
Safety analysis set (SAS)	All participants randomly assigned to study intervention and who take at least 1 dose of study intervention. Participants will be analyzed according to the study intervention they received.
mITT	All participants randomly assigned to study intervention who take at least 1 dose of study intervention and who have a positive viral RNA NP swab test result ($\geq 2.0 \log_{10}$ copies/mL) at baseline. Participants will be analyzed according to the study intervention they were randomized.
Per protocol (PP)	All participants in the mITT analysis set without important protocol deviations considered to impact the interpretation of the primary efficacy endpoint. Protocol deviations will be reviewed to generate the list of participants with significant deviations to be excluded from the PP analysis set. The PP exclusion criteria will be finalized prior to breaking the blind.
mITT1	All participants randomly assigned to study intervention who take at least 1 dose of study intervention and who have a positive rapid antigen test result at baseline. Participants will be analyzed according to the study intervention they were randomized.

The primary analysis set for efficacy will be the mITT. mITT1 will be used for relevant efficacy endpoints. Safety Analysis Set (SAS) will be used in the analyses of the safety data.

All participants from CCI [REDACTED] will be excluded from the efficacy analyses due to GCP issues.

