Number of COVID-19-related medical visits through Day 34	Exploratory	mITT	Missing data will not be imputed.	Descriptive summary
Time (days) to sustained resolution of all targeted signs and symptoms through Day	Exploratory	mITT mITT1	Missing data will not be imputed.	Cox proportional hazard model; KM curves
Concordance analysis of RAT and SARS-CoV-2 viral RNA level in NP swabs	Other	mITT1	Missing data will not be imputed.	Descriptive summary

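### Kappa between the antigen test and RT-PCR is planned only on data pooled over visits, so part of the decline that both tests share over time is scored as agreement beyond chance

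*SAP*

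**What the plan says.** SAP 6.3.12 pairs rapid antigen and NP swab RT-PCR results from the same study day, in mITT1, by arm and combined. It states that "the concordance analysis will be performed at each visit, across post-baseline visits and across all visits". Kappa is narrower: "Kappa statistic will be provided as a measurement of agreement between rapid antigen test and RT-PCR for across post-baseline visits and across all visits". No kappa within a visit, stratification by visit or confidence interval is mentioned. Appendix 1 lists "Concordance analysis of RAT and SARS-CoV-2 viral RNA level in NP swabs" as an analysis of type Other, with a descriptive summary.

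Three other passages determine what enters the pooled tables:

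- mITT1 (SAP section 4) contains participants "who have a positive rapid antigen test result at baseline", so antigen positivity at baseline is 100% by definition.
- RNA is assessed "below the LLOQ on Days 3, 5, 10, 15, 21, 28, and 34" (SAP 3.3), which gives seven post-baseline visits.
- After two consecutive negative antigen results daily testing stops, but antigen "testing will be done at regularly scheduled onsite visits" (Protocol 1.3). Late visits, where few positives are expected, therefore still supply pairs.

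**The concern.** Kappa subtracts the agreement expected by chance, and it calculates that expectation from the overall positive rates in the table it is given. In a table stacking Days 3 to 34, those rates are averages over early visits with many positives and late visits with few. Two results from the same early visit then tend to be both positive, and two from the same late visit both negative, simply because of when they were taken. Kappa credits this to the tests.

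The antigen test defines a secondary endpoint in the Hochberg step, and NP RNA is the primary endpoint. A reader of the study report may take the kappa as evidence of how well one stands in for the other in the same person on the same day. A pooled kappa mixes that with the common time course, and no chance-corrected measure is planned that separates the two.

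**Working it through.** **Plan's own figures.** The documents state no kappa and no positivity by visit after baseline, so there is no planned kappa to reproduce. The one usable rate is at baseline: "Assuming approximately 10% of participants will have a negative viral RNA result at baseline" (SAP 2.4), that is, about 90% RNA positive. It is the rate behind the enrolment figure: 315/(0.90 × 0.85) = 411.8, against 411 stated.

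**Formula.** Let a_v and b_v be the antigen and RNA positive rates at visit v, with visits weighted equally and means A and B. Suppose the tests are independent within every visit, so that true chance-corrected agreement is zero throughout. Then

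- po = mean of [a_v b_v + (1 − a_v)(1 − b_v)]
- pe = AB + (1 − A)(1 − B)
- pooled kappa = (po − pe)/(1 − pe)
- po − pe = 2 × [mean(a_v b_v) − AB], twice the covariance of the two rates over visits.

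This is zero if either rate is constant over visits and positive whenever both fall together.

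**Middle case (assumed rates, Days 3, 5, 10, 15, 21, 28, 34).** Antigen 90, 70, 20, 5, 2, 1, 1%; RNA 88, 80, 50, 30, 20, 10, 8%.

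- Post-baseline: A = 0.270, B = 0.4086, mean(a_v b_v) = 0.2104. po − pe = 2 × (0.2104 − 0.1103) = 0.2002; pe = 0.5421. Kappa = 0.2002/0.4579 = **0.44**.
- All visits (baseline 100% and 90% added): A = 0.36125, B = 0.470, mean(a_v b_v) = 0.2966. po − pe = 2 × (0.2966 − 0.1698) = 0.2536; pe = 0.5083. Kappa = 0.2536/0.4917 = **0.52**.

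Baseline carries no information on chance-corrected agreement, because every antigen result there is positive. Adding it still raises the value.

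**Range over assumed curves, chance-only agreement at every visit** (baseline as above):

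| Assumed curves | Antigen % | RNA % | Post-baseline | All visits |
|---|---|---|---|---|
| Middle | 90/70/20/5/2/1/1 | 88/80/50/30/20/10/8 | 0.44 | 0.52 |
| Fast antigen clearance | 80/50/10/2/1/1/1 | 85/70/35/20/10/5/5 | 0.43 | 0.54 |
| Slow RNA clearance | 90/70/20/5/2/1/1 | 90/88/70/50/35/25/20 | 0.32 | 0.39 |
| Very slow RNA clearance | 80/50/10/2/1/1/1 | 90/88/75/60/50/40/30 | 0.18 | 0.25 |
| Similar curves | 90/75/30/10/3/2/1 | 88/78/40/15/8/5/3 | 0.53 | 0.60 |
| Steep common decline | 95/85/20/2/1/0.5/0.5 | 90/88/35/10/5/3/2 | 0.66 | 0.71 |
| Low antigen | 60/35/5/1/1/1/1 | 80/65/40/25/15/10/10 | 0.27 | 0.42 |
| Flat decline | 60/40/15/5/3/2/2 | 75/65/50/40/30/25/20 | 0.17 | 0.30 |

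A sweep of 20,000 assumed logistic declines gave a post-baseline median of 0.46 (central 95% 0.31 to 0.65) and an all-visits median of 0.55 (0.44 to 0.70).

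**Does pooled kappa respond to true agreement?** Keep the middle-case margins and let the tests agree as often as the margins allow, po_v = 1 − |a_v − b_v|. The differences sum to 1.01, so po = 1 − 1.01/7 = 0.8557, and post-baseline pooled kappa = (0.8557 − 0.5421)/0.4579 = 0.68. It therefore runs from 0.44 (chance only) to 0.68 (maximum attainable).

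**Stratified alternative.** Take sum(po_v − pe_v)/sum(1 − pe_v) over the seven visits, with pe_v computed within each visit. Here the pe_v sum to 5.1956.

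- Chance only: numerator 0, kappa 0. One simulated data set with 385 participants per visit gave 0.01, against 0.43 for the post-baseline pooled kappa.
- Maximum agreement: (5.99 − 5.1956)/(7 − 5.1956) = 0.44.

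**The case against.** SAP 6.3.12 gives no purpose for the kappa. If the aim is to describe whether the two tests follow the infection together, both turning negative is part of the answer, and pooling is a choice of target, not a mistake. This stands in part: the pooled kappa may stay, provided its label says that it includes the time course.

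Concordance is also planned at each visit. If that is shown as a full cross-tabulation, anyone can derive kappa or percent agreement by visit. That is fair, although the SAP does not say what the per-visit output contains.

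Within-visit kappa has its own limits. At the middle-case margins for Days 15 to 34, even if every antigen-positive sample is RNA-positive, kappa reaches only 0.15 to 0.22 because the positive rates differ. A stratified kappa inherits part of this, so it should sit beside the pooled kappa and percent agreement and not replace them.

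Full independence within visits is an extreme benchmark for two tests of the same virus on the same day. It locates the floor; it is not a forecast.

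A reader might also object that up to seven pairs per participant are treated as independent, or that arms clearing at different speeds would make a comparison of kappas misleading. Neither has a target in the plan: no confidence interval or test for kappa and no comparison between arms is planned.

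**Conclusion.** The point holds as an improvement to a descriptive analysis. Pooling inflates kappa whenever both positive rates fall over the visits. The direction follows from the formula; the size rests on assumed post-baseline rates, equal visit weights, and RNA positivity taken as at or above the LLOQ (6.3.12 names no cut). On those assumptions the floor is about 0.2 to 0.7, with a middle case of 0.44 post-baseline and 0.52 over all visits.

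Two stronger readings are not supported. A reader might infer that the trial would report some particular narrow range, such as 0.3 to 0.5, for tests with no same-day agreement; the documents give no rates from which to derive one, and plausible curves fall on both sides. A reader might also infer that the pooled kappa looks good whatever the true agreement is. It does not: in the middle case it moves from 0.44 to 0.68 as agreement goes from chance to the attainable maximum.

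No hypothesis, alpha allocation or estimand depends on this kappa.

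**What to change.** In SAP 6.3.12 and the matching row of Appendix 1:

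1. Add a visit-stratified kappa over the post-baseline visits, for example sum(po_v − pe_v)/sum(1 − pe_v), overall and by arm, beside the pooled kappa. A visit with no antigen positives has po_v = pe_v, so it adds nothing to the numerator and the ratio stays defined. Inverse-variance weights should be avoided: at such a visit the estimated variance is 0 and the weight is infinite. At an assumed 1% antigen positivity in 137 placebo participants (411/3), the chance of no positives at a visit is 0.99^137 = 0.25.
2. Leave baseline out of the chance-corrected measure.
3. Give positive and negative percent agreement at each visit.
4. Label the pooled kappa as descriptive agreement that includes the common time course.
5. If a confidence interval is given, obtain it from a bootstrap that resamples participants.

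The cost is a few lines of SAP text and a little programming, with no new data. The downside is a lower reported kappa, itself limited by the differing positivity of the two tests at late visits.

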6.4. Subset Analyses

Subgroup analyses of the primary endpoint (if data permitted) will include:

- Age group (<18, 18 to <60, ≥ 60) and (<65, ≥ 65);
- Gender;
- Race;
- Ethnicity;
- BMI category (<25, 25 to <30, ≥ 30);
- Baseline viral load ($<7 \log_{10}$ copies/mL, $\geq 7 \log_{10}$ copies/mL; $<4 \log_{10}$ copies/mL, $\geq 4 \log_{10}$ copies/mL);
- Geographic region (US, Ex-US) .

A forest plot will display confidence intervals across subgroups.

6.5. Baseline and Other Summaries and Analyses

6.5.1. Baseline and Other Characteristics Summaries

The baseline and demographic characteristics will be summarized by treatment group within the FAS and other analysis set as appropriate. This will include age, gender, race, height, and baseline weight, etc. Other characteristics including household characteristics will also be summarized by treatment group within the FAS.

6.5.2. Study Conduct and Participant Disposition

Study conduct and participant disposition will be summarized within the FAS. The number of participants randomized, treated, completing and discontinuing from the study, as well as the number of participants in each analysis set will be summarized by treatment group. For participants who did not complete the study, the reasons for withdrawal from the study will be presented.

6.5.3. Study Treatment Exposure

Duration of treatment will be summarized within the SAS.

The duration of treatment will be calculated as follows: Duration of treatment = Date of last dose of study drug - date of first dose of study drug +1.

Compliance over the whole treatment period will be calculated as follows:

$$\text{Compliance} = \frac{\text{Actual Number of Doses Received}}{\text{Planned Number of Doses}} * 100$$

A participant is considered compliant if between 80% and 115% of the planned number of doses is received. The compliance will be summarized in the following categories: <80%, 80% to 115%, and >115% by the number and percentage of participants in each treatment group.

6.5.4. Prior and Concomitant Medications

The frequency of prior and concomitant medications will be summarized by treatment based on the WHO-drug coding dictionary within the SAS in accordance with Clinical Data Interchange Standards Consortium (CDISC) and Pfizer Standards (CaPS).

6.6. Safety Summaries and Analyses

Standard summary tables and listings will be generated in accordance with CDISC and CaPS for safety reporting for the following parameters: AEs, laboratory parameters, and vital signs.

6.6.1. Adverse Events

AEs will be coded according to the Medical Dictionary for Regulatory Activities (MedDRA) and will be summarized by treatment group within the SAS.

6.6.2. Laboratory Data

Laboratory values and the corresponding changes from baseline will be summarized with descriptive statistics by treatment group in the SAS. Laboratory data will be reported in accordance with CDISC and CaPS for safety reporting.

6.6.3. Vital Signs

Vital sign data and the corresponding changes from baseline will be descriptively summarized by treatment within the SAS. Vital sign data will be reported in accordance with CDISC and CaPS.

